
Primary
 
 • Demonstrate the superiority of CVC compared to placebo on the composite endpoint of histopathologic progression to cirrhosis, liver-related clinical outcomes, and all-cause mortality, as measured by the time to first occurrence of any of the listed adjudicated events (clinical outcomes composite endpoint) – (all subjects) 	
Primary Endpoint
 
Time to first occurrence of any of the following adjudicated events:
 
 • Death (all cause) • Histopathologic progression to cirrhosis (i.e., NASH CRN fibrosis stage 4) • Liver transplant • MELD score ≥ 15 • Ascites (requiring intervention, i.e., large volume paracentesis $\geq 1L$ or initiation of a diuretic) • Hospitalization (as defined by a stay of ≥ 24 hours) for onset of: variceal bleed, hepatic encephalopathy (defined by a West Haven Stage of ≥ 2), spontaneous bacterial peritonitis (confirmed by diagnostic paracentesis with positive ascitic fluid bacterial culture) 
Each component of this endpoint will be considered by the independent adjudication committee, and only events confirmed by the committee will be included in the primary analysis.
 
If any of the above events occurs in Part 1, they will be included in this primary efficacy endpoint for Part 2.

Secondary
 
 • To evaluate the effect of CVC compared to placebo on liver histology at Month 12 relative to the Screening biopsy for the proportion of subjects with improvement in fibrosis by at least 1 stage (NASH CRN system) AND no worsening of steatohepatitis (no worsening of lobular inflammation or hepatocellular ballooning grade 2005) – (subjects newly randomized in Part 2) 	
Secondary Endpoints
 
 • Improvement in fibrosis by at least 1 stage (NASH CRN system) AND no worsening of steatohepatitis (no worsening of lobular inflammation or hepatocellular ballooning grade 2005) on liver biopsy at Month 12 relative to the Screening biopsy – (subjects newly randomized in Part 2)

Objectives: Global Part 2	Endpoints: Global Part 2

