5.1.1.1 Common Conventions

5.1.1.1.1 Analysis Populations

The analysis populations will consist of subjects as defined below:

Table 5-1 Analysis Populations

Population	Definition	Study Treatment
Screened	All screened subjects who sign informed consent.	—
Intent-to-Treat (ITT)	All randomized subjects will be included in the randomly assigned treatment group, even if they receive a different treatment from that to which they are randomly assigned. This will be a supportive analysis set for selected efficacy analyses. Subjects with missing Screening biopsy data should not be randomized in the study, and hence will not be included in the ITT analysis set, should such subjects exist.	Randomized assignment
Modified Intent-to-Treat (mITT)	All randomized subjects who receive ≥ 1 dose of study drug will be included in the randomly assigned treatment group, even if they receive a different treatment from that to which they are randomly assigned. This will be the primary analysis set for the efficacy analyses.	Randomized assignment
Month 12 per protocol (PP1)	All subjects randomly assigned to a treatment group who have an evaluable biopsy at Screening and another after at least 6 months but before 15 months of follow-up, receive at least 6 months of assigned study drug and have no significant protocol deviations that potentially influence the primary efficacy assessment will be included in the PP1 analysis set. This will be a supportive analysis set for selected efficacy analyses of Part 1 and Part 2.	Randomized assignment

Population	Definition	Study Treatment

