Month 60 per protocol (PP2)	
All subjects randomly assigned to a treatment group who have an evaluable biopsy at Screening, have no significant protocol deviations that potentially influence the primary efficacy assessment, and either:
 
 • Have an adjudicated event that is a component of the primary composite endpoint within 24 months after randomization 
OR
 
 • Have at least 24 months of follow-up for clinical events AND one of the following: 
 • Have an adjudicated event that is a component of the primary composite endpoint within 6 months of last intake of study drug 
OR
 
 • Have a biopsy at least 24 months after randomization and within 6 months of last intake of study drug. 
This will be a supportive analysis set for selected efficacy analyses of Part 2.
	Randomized assignment
Safety	
All subjects who received ≥ 1 dose of study drug will be included in the safety analysis set. Subjects will be included in the treatment group according to actual treatment received, even if they receive a different treatment than that to which they are randomly assigned. Subjects who inadvertently receive both treatments will be included with the CVC group.
 
This will be the primary analysis set for the safety analyses.
	Actual received ¹
Pharmacokinetic	All subjects who are randomized and receive at least one dose of study drug and have at least one post-dose PK sample will be included in the PK analysis set.	Randomized assignment

¹ Subjects will be summarized according to the study treatment received.

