5.1.1.2.3 Protocol Deviations

Significant protocol deviations will be summarized for the ITT population (i.e., all randomized subjects) as follows:

Table 5-7 Protocol Deviation Summary

Parameter	Description	Timing	Methodology
Significant protocol deviations	
Distribution in the ITT Population in total and by treatment group
 
The set of subjects excluded from the PP1 analysis set will be identified prior to database lock and unblinding the study database for Part 1. Additional subjects may be included or excluded in the PP1 set for analysis of Part 2 if subjects are randomized to Part 2 after the analysis of Part 1 or if additional significant protocol deviations are identified between Part 1 analysis and unblinding of the study database for Part 2. The set of subjects excluded from the PP2 analysis set will be identified prior to database lock and unblinding the study database for Part 2.
	—	Categorical descriptive statistics

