Part 2: Primary efficacy endpoint (sensitivity analysis 3)	Analysis of the primary endpoints for Part 2 will also use the Cochran-Mantel-Haenszel (CMH) test, stratified by true fibrosis stage (2, 3) and T2DM status (presence, absence) at baseline, for a total of 4 strata, to compare the event rates in the 2 randomized treatment arms.	Same as above	Cochran-Mantel-Haenszel (CMH) test, stratified by true fibrosis stage (2, 3) and T2DM status (presence, absence) at baseline
Part 2: Primary efficacy endpoint (sensitivity analysis 4)	An assessment of primary endpoint will also be made using imputation of subjects censored without an event before 5 years of follow-up	Same as above	Time-to-event Logrank test

Type of Endpoint	Description	Timing	Methodology
Part 2: Secondary efficacy endpoints (binary)	
Analysis of secondary efficacy endpoints of Part 2 will use similar methods to the primary endpoint analysis in Part 2. The primary endpoint in Part 1, improvement in fibrosis by at least one stage and no worsening of steatohepatitis at Month 12, will be reported for subjects not in the Part 1 analysis (subjects newly randomized in Part 2), and for all subjects in the study (Month 12 results from Part 1 and Part 2 combined).
 
Results for the mITT and PP2 analysis sets will be reported for the secondary endpoints in Part 2. Binary endpoints will be analyzed with the CMH procedure, stratified by true fibrosis stage (2, 3) and T2DM status (presence, absence) at baseline.
	Same as above	Cochran-Mantel-Haenszel (CMH) test, stratified by true fibrosis stage (2, 3) and T2DM status (presence, absence) at baseline

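### The Month 12 secondary endpoints in Part 2 are assigned to the Month 60 per-protocol set (PP2), which is not a per-protocol check of a Month 12 result; PP1 is the set built for it

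*SAP*

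**What the plan says.** **Endpoints.** SAP 4.2 lists eight secondary efficacy endpoints for Part 2. Four are fibrosis responses assessed at Month 12 in newly randomised subjects (for example, "on liver biopsy at Month 12 relative to the Screening biopsy"). The other four are the Month 60 counterparts in all subjects.

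**Analysis sets.** SAP Table 5-14 (section 5.1.1.3.1) and protocol 12.3.2.2 both say: "Results for the mITT and PP2 analysis sets will be reported for the secondary endpoints in Part 2". The sentence just before it concerns the Month 12 response, both for newly randomised subjects and for Parts 1 and 2 combined, so the rule plainly reaches those analyses.

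**PP2** (SAP Table 5-1; protocol 12.1.1) needs an evaluable Screening biopsy, no significant deviation, and one of two routes:
- Route 1: "Have an adjudicated event that is a component of the primary composite endpoint within 24 months after randomization".
- Route 2: "Have at least 24 months of follow-up for clinical events", together with either (a) "Have an adjudicated event that is a component of the primary composite endpoint within 6 months of last intake of study drug" or (b) "Have a biopsy at least 24 months after randomization and within 6 months of last intake of study drug".

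**PP1** needs an "evaluable biopsy at Screening and another after at least 6 months but before 15 months of follow-up", plus at least 6 months of assigned drug. It is declared supportive for both parts of the study. SAP Table 5-7 plans to update it for Part 2: "Additional subjects may be included or excluded in the PP1 set for analysis of Part 2 if subjects are randomized to Part 2".

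**The concern.** A per-protocol analysis should ask whether the result holds among subjects who took the treatment and were assessed as planned for that endpoint. PP2 asks something else. Nothing in it requires the Month 12 assessment, and it selects on events or on follow-up beyond Month 12. Part of that selection depends on the endpoint itself: a Month 12 biopsy can be both the response reading and, if it shows cirrhosis, the event that admits the subject. A reader of the clinical study report would take the PP2 row as a robustness check on the Month 12 response, when it is a comparison in a group formed partly by later outcomes.

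**Working it through.** The plan gives no figure on this point. The check sets the definitions side by side and then sizes the effect.

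**1. Definitions against a Month 12 endpoint**

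| | PP1 | PP2 |
|---|---|---|
| Biopsy around Month 12 | required (6 to 15 months) | not required |
| Minimum drug exposure | 6 months | none |
| Depends on events or later follow-up | no | yes |
| Secondary endpoints assigned to it in Table 5-14 | Part 1, all at Month 12 | Part 2, at Month 12 and Month 60 |

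**2. Cases (no significant deviation)**
- *Month 12 responder, valid on-treatment biopsy, leaves event-free at Month 20.* In PP1. Fails both PP2 routes.
- *Month 12 biopsy read as Stage 4 and confirmed by the adjudication committee.* Newly randomised subjects all start at Stage 3 (protocol 8.2, criterion 4), so this is a certain non-response. It is also an event within 24 months, so the subject enters PP2 by route 1.
- *No biopsy between 6 and 15 months, confirmed event at Month 18.* Out of PP1, in PP2.

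**3. Planning inputs for sizing** (SAP 5.1.2): 80% event-free on placebo at Month 60, hazard ratio 0.62, 367 events; Month 12 response 25% v 15%.
- The event inputs are coherent. Power = Φ(√(367 × 2/9) × |ln 0.62| − z) = Φ(4.317 − 3.227) = 86.2% at 0.00125 (stated 85%), and 99.1% at 0.05 (stated 99%).
- CVC events at Month 60: 1 − 0.80^0.62 = 12.9%.
- Events by Month 24 (exponential curve), which open route 1: placebo 1 − 0.80^(24/60) = 8.5%; CVC 1 − 0.80^(0.62 × 24/60) = 5.4%.

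**4. Shift under planned event rates, equal retention across arms.** Assumptions not in the documents: every subject with an event is kept; a share q of event-free subjects qualifies by late biopsy; responders have events at 20/35 the rate of non-responders.
- Placebo: non-responders 0.20/(0.15 × 20/35 + 0.85) = 21.4%, responders 12.2%.
- CVC: non-responders 0.129/(0.25 × 20/35 + 0.75) = 14.5%, responders 8.3%.
- Inclusion probability i = e + (1 − e)q. PP2 response = p·iR / (p·iR + (1 − p)·iN).

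| q | CVC | Placebo | Difference |
|---|---|---|---|
| 0.2 | 21.9% | 12.4% | 9.5 points |
| 0.5 | 24.0% | 14.0% | 9.9 points |
| 0.8 | 24.7% | 14.7% | 10.0 points |

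The true difference is 10 points.

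**5. No true difference.** Assume the same response in both arms (15% or 25%), all events by Month 24 in non-responders, and 40% to 80% of other subjects qualifying by route 2. PP2 then shows a spurious CVC advantage of 0.1 to 1.0 points. If route 2 qualification among non-responders differs by arm by 10 points (50% v 60%; responders 70%; response 15%), the spurious difference is −1.8 points when placebo has the lower share and +2.7 points when CVC does.

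**The case against.** The strongest reply is that little rides on this. mITT is the primary efficacy set and PP2 is only supportive. SAP 5.1.1.3.3 allocates alpha to the Part 1 surrogate endpoints and the Part 2 clinical outcome, and none to these endpoints. The documents already point to PP1 for Part 2, so this may be a drafting slip. All of that stands, and it limits the consequence. It does not make the written rule right.

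Four stronger readings are tempting, and the documents do not support them.
- *A large bias.* If 35% of non-responders and 20% of responders later had events, and q were 0.2, PP2 would show 20.0% v 11.7%, a difference of 8.3 points. Those rates imply events in 31.3% of CVC and 32.8% of placebo subjects: about 635 events in 2000 and a hazard ratio near 0.94, against the planned 367 and 0.62. A q of 0.2 is also low when a Month 60 biopsy is scheduled for everyone and planned dropout is 20%.
- *Selection always lies years after the endpoint.* Route 1 can be met at or before Month 12. Route 2 looks at least 12 months past Month 12, and 48 months past it when met by the Month 60 biopsy.
- *A PP2 member without a Month 12 biopsy is scored a non-responder.* SAP Table 5-2 treats a missing post-baseline biopsy that way in general, but Table 5-4 has no row for Part 2 Month 12 responders. Whether a later biopsy would be used instead is open. mITT also keeps such subjects.
- *The PP2 result is worthless as evidence.* A shift of half a point or less under planned rates does not support that.

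**Conclusion.** The point holds in limited form. As written, both documents attach the Month 60 per-protocol set to Month 12 endpoints, and the result would not be a per-protocol check of them. The mITT result is unaffected.

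Under planned event rates and equal retention across arms, a 10-point difference moves by about 0.5 points or less for q from 0.2 to 0.8. With retention differing by arm, the illustration above gives roughly −2 to +3 points. These sizes rest on assumed retention and on an assumed link between response and later events. The planning rates cover the whole study, whereas newly randomised subjects are all Stage 3, and the documents give no separate Stage 3 event rate. The case rests on the mismatch of set and endpoint, not on a particular bias.

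**What to change.** In SAP Table 5-14 (Part 2 secondary efficacy endpoints), protocol 12.3.2.2 and the matching synopsis text, replace the sentence with: *mITT and PP1 for Month 12 endpoints (newly randomised subjects, and Parts 1 and 2 combined); mITT and PP2 for Month 60 endpoints.*

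Also reconcile the Part 2 primary endpoint in Table 5-14. Sensitivity analyses 1 names ITT and PP1 for the time-to-event analysis, while the main description in the same table names ITT and PP2. The two per-protocol labels may have been interchanged.

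The cost is a sentence per location. Updating PP1 for Part 2 subjects is already planned, so no new data or derivation is needed. Making the change before Part 2 unblinding avoids a post hoc choice of set.

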5.1.1.3.3 Multiple Comparisons Procedure for Primary and Secondary Endpoints

The significance level of both 0.00125 (2-sided) and 0.05 (2-sided) will be applied to hypothesis testing in this study, with the former to manifest strong evidence from a single confirmatory study and the latter for study success. Alpha splitting will be applied for multiplicity adjustment. The above applies for both global and EU-specific analyses.

To manifest strong evidence from a single confirmatory study, the familywise type I error rate (between the surrogate endpoint and the clinical outcome endpoint) will be controlled at the 0.00125 level by initial assignment of 0.0012 to the surrogate endpoint and 0.00005 to the clinical outcome endpoint, and the clinical outcome endpoint will be tested at the 0.00125 level if the tests of the surrogate endpoints (i.e., primary and key secondary) are successful. The testing procedure will be the same for study success, except the familywise type I error rate will be controlled at the 0.05 level instead of 0.00125 level, in which an initial alpha level of 0.048 to the surrogate endpoint and of 0.002 to the clinical outcome endpoint will be allocated.

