
Efficacy Part 1
	
The significance level of both 0.00125 (2-sided) and 0.05 (2-sided) will be applied to hypothesis testing in this study, with the former to

	
manifest strong evidence from a single confirmatory study and the latter for study success.
 
To manifest strong evidence from a single confirmatory study, the familywise type I error rate (between the surrogate endpoint and the clinical outcome endpoint) will be controlled at the 0.00125 level by initial assignment of 0.0012 to the surrogate endpoint and 0.00005 to the clinical outcome endpoint, and the clinical outcome endpoint will be tested at 0.00125 level if the test of surrogate endpoint is successful. The testing procedure will be the same for study success, except the familywise type I error rate will be controlled at the 0.05 level instead of 0.00125 level, in which an initial alpha level of 0.048 to the surrogate endpoint and of 0.002 to the clinical outcome endpoint will be allocated.
 
The primary analysis of Part 1 will occur when approximately 1200 randomized subjects have been followed for at least 12 months. Subjects who will contribute to the primary analysis of Part 1 will be identified before unblinding of any subjects for Part 1 analysis. Individual subjects' treatment group assignments will not be disseminated to the sites until the end of Part 2 to allow for continued blinded assessment during Part 2.
 
For the primary efficacy analysis in Part 1, using the mITT analysis set, any available liver biopsy after baseline will be used as the Month 12 biopsy, no matter when it was obtained relative to the first dose of study drug. Subjects who do not have an evaluable liver biopsy at both Screening and Month 12 will be included in the analyses as non-responders. Subjects with multiple liver biopsies will have the evaluable biopsy closest to the Month 12 visit included in the analysis.
 
The proportion of subjects who meet the primary efficacy endpoint in Part 1, and each component, will be summarized by treatment group. Two-sided 95% confidence intervals (CI) for the proportion who meet the primary efficacy endpoint, calculated using Wilson's method for CI, will also be reported.
 
Part 1 testing hierarchy includes 2 tests, one for the primary endpoint and the other for the key secondary endpoint. Within Part 1 testing, the key secondary endpoint is to be tested only when the primary endpoint result is significant.
 
Analysis of the primary and the key secondary endpoints of Part 1 will use the Cochran-Mantel-Haenszel (CMH) test, stratified by randomization strata (fibrosis stage [2 vs 3] and presence or absence of T2DM at Baseline, for a total of 4 strata), to compare the rates in the 2 randomized treatment arms.
 
Sensitivity analyses for the primary efficacy endpoint will also be performed. Subgroup analyses using the CMH test will be reported for selected subgroups.
 
Analysis of other secondary efficacy endpoints of Part 1 will use similar methods to the primary endpoint analysis. Results for the mITT and PP1 analysis sets will be reported for secondary efficacy endpoints. Binary endpoints will be analyzed with the CMH procedure, stratified by randomization strata. Continuous endpoints will be analyzed with

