#### **5.4. Study Rationale**

The clinically important results from the Phase 2b CENTAUR study are robust and suggest that CVC treatment may be disease modifying in adult patients with liver fibrosis as a result of NASH. This is particularly relevant when considering the comprehensive and clinically evidence which demonstrates that liver fibrosis, regardless of other histological components of steatohepatitis, is the only histologic feature independently associated with all-cause mortality and liver-related outcomes in patients with NAFLD. Cenicriviroc appears to be safe with no notable differences observed in previous clinical studies in incidence of treatment-emergent AEs and laboratory abnormalities, including liver transaminase elevations, which were generally similar between treatment groups.

The AURORA study (Protocol 3152-301-002) will be conducted to confirm the efficacy and safety of CVC for the treatment of liver fibrosis in adult subjects with NASH.

The study will be conducted in 2 parts:

- Part 1: Evaluate the surrogate endpoint of improvement in fibrosis of at least 1 stage (nonalcoholic steatohepatitis clinical research network [NASH CRN]) and no worsening of steatohepatitis at Month 12 in subjects with Stage 2 and 3 liver fibrosis.
- Part 2: Determine the long-term clinical outcomes composed of histopathologic progression to cirrhosis (defined by NASH CRN Fibrosis Stage 4), liver-related clinical outcomes, and all-cause mortality in subjects from Part 1 who have continued into Part 2 and additional newly randomized subjects with a liver biopsy diagnosis of NASH and Stage 3 liver fibrosis enrolled in Part 2.

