5.1.1.1.7 Other Common Conventions

Continuous data will be described with sample size, mean, standard deviation, median, minimum and maximum. Categorical data will be described with frequencies and percentages in each category. Two-sided p-values for all hypothesis tests will be reported and will be interpreted in accordance with the multiple comparisons procedure described in Section 5.1.1.3.3.

Subjects will be enrolled in 2 parts, Part 1 and Part 2. Only subjects randomized for Part 1 will contribute to the Part 1 analyses, and all randomized subjects (i.e., subjects randomized for Part 1 and subjects randomized for Part 2) will contribute to the Part 2 analyses. When subjects who contribute to Part 1 have completed their 12-month biopsy (or have been followed for a sufficient time to confirm that such a biopsy will not be obtained), the Part 1 analysis will commence. The Part 1 analysis will summarize subject disposition, significant protocol deviations, study intervention exposure, concomitant medications, demographics and baseline characteristics, efficacy through the Month 12 visit, and safety for subjects enrolled in Part 1, including all available safety data in the database at the time of the Part 1 database lock. At the completion of the entire study, analyses will be provided for all subjects randomized, including all available data in the database.

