Part 2: Primary efficacy endpoint: Time to first occurrence of adjudicated events	Date of Baseline visit will be used in the calculation for time to first occurrence of any of the following adjudicated event endpoints: 
 • Death (all cause) • Histopathologic progression to cirrhosis (based on NASH CRN fibrosis stage 4) • Liver transplant • MELD score ≥ 15 • Ascites (requiring intervention, i.e., large volume paracentesis $\geq 1L$ or initiation of a diuretic) • Hospitalization (as defined by a stay of ≥ 24 hours) for onset of: variceal bleed, hepatic encephalopathy (defined by a West Haven Stage of ≥ 2), spontaneous bacterial peritonitis (confirmed by diagnostic paracentesis with positive ascitic fluid bacterial culture) If any of the adjudicated events occur in Part 1, they will be included in the primary efficacy endpoint for Part 2.	For subjects newly randomized in Part 2: Date of Baseline visit in Part 2 For subjects continuing from Part 1: Date of Baseline visit in Part 1

Type of Endpoint	Description	Timing
Part 2: Secondary efficacy endpoint (for subjects newly randomized in Part 2): Improvement of fibrosis stage (NASH CRN system) on liver histology at Month 12 relative to the Screening biopsy	Fibrosis stage (NASH CRN system) based on Screening biopsy.	Screening biopsy result before Baseline visit and before subject is randomized in Part 2
Part 2: Secondary efficacy endpoint (for subjects newly randomized in Part 2): Worsening of steatohepatitis (no worsening of lobular inflammation or hepatocellular ballooning grade 2005) on liver histology at Month 12 relative to the Screening biopsy	NAFLD activity score (NAS) components based on Screening biopsy.	Screening biopsy result before Baseline visit and before subject is randomized in Part 2

5.1.1.3.1 Endpoint Domain 1

The testing hierarchy is as follows for the Part 1 analyses:

[figure not shown]
- Global: Part 1 testing hierarchy includes 2 tests, one for the primary endpoint and the other for the key secondary endpoint, which are both binary endpoints. The key secondary endpoint is tested only when the primary endpoint result is significant. These surrogate endpoints will be tested at the 0.0012 (2-sided) alpha level to manifest strong evidence from a single confirmatory study, and 0.048 (2-sided) level for study success.

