- Region-specific Europe: Part 1 testing is only for the region-specific primary endpoint, a binary endpoint. The surrogate endpoint will be tested at the 0.0012 (2-sided) alpha level to manifest strong evidence from a single confirmatory study, and 0.048 (2-sided) level for study success.

The general description of the domains of clinically-related endpoints is stated below.

Table 5-14 Domain 1 Analyses

Type of Endpoint	Description	Timing	Methodology
Part 1: Primary efficacy endpoint (binary)	
For the primary efficacy analysis in Part 1, using the mITT analysis set, any available liver biopsy after baseline will be used as the Month 12 biopsy, no matter when it was obtained relative to the first dose of study drug. Subjects who do not have an evaluable liver biopsy at both Screening and Month 12 will be included in the analyses as nonresponders. Subjects with multiple liver biopsies will have the evaluable biopsy closest to the Month 12 visit included in the analysis.
 
The proportion of subjects who meet the primary efficacy endpoint in Part 1, and the proportion who meet each component of the primary efficacy endpoint, will be summarized by treatment group. Two-sided 95% CIs for the proportion of subjects who meet the primary efficacy endpoint, calculated using Wilson's method for CI, will be reported.
 
Analysis of the primary and key secondary endpoints of Part 1 will use the Cochran-Mantel-Haenszel (CMH) test, stratified by true fibrosis stage (2, 3) and T2DM status (presence, absence) at baseline, for a total of 4 strata, to compare the rates in the 2 randomized treatment arms.
	
Screening, Month 12
 
The primary analysis of Part 1 will occur when approximately 1200 randomized subjects have been followed for at least 12 months. Subjects who will contribute to the primary analysis of Part 1 will be identified before unblinding of any subjects for Part 1 analysis; subjects who will not contribute to the primary analysis of Part 1 will be identified by date of randomization. Individual subjects' treatment group assignments will not be disseminated to the sites until the end of Part 2 to allow for continued blinded assessment during Part 2.
	
Responder
 
Two-sided 95% CIs for responder using Wilson's method for CI.
 
Cochran-Mantel-Haenszel (CMH) test, stratified by true fibrosis stage (2, 3) and T2DM status (presence, absence) at baseline

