
Part 2: Primary efficacy endpoint (time-to-event)
	
Time-to-event analyses will be performed using the Kaplan-Meier product-limit method with tabular and graphical presentation for the cumulative probability of event rate by treatment group. Subjects will be censored for analysis at the last recorded study visit.
 
Analysis of the primary endpoint of Part 2 will use the logrank test, stratified by true fibrosis stage (2, 3) and T2DM status (presence, absence) at baseline, for a total of 4 strata, to compare the rates in the 2 randomized treatment arms. If multiple adjudicated events are observed in a single subject, only the first observed event will be used in the analysis. The analysis will use the mITT analysis set, with supportive analyses reported for the
	
Same as above
	
Time-to-event KM figure

Type of Endpoint	Description	Timing	Methodology
Part 2 (Global/Region-specific Europe): Testing (primary endpoint) (time-to-event)	
ITT and PP2 analysis sets. Subjects who do not have an adjudicated event will be censored for analysis at the last recorded study visit. The p-value for the test of no difference between treatment arms (hazard ratio=1) will be presented as well as the hazard ratio from a proportional hazards model (CVC divided by placebo) and corresponding 95% CI.
 
Global/Region-specific Europe: To manifest strong evidence from a single confirmatory study, the hypothesis test of clinical endpoint will be performed at a significance level of 0.00125 (2-sided) if the test of the surrogate endpoint is successful and 0.00005 (2-sided) otherwise. For study success, the hypothesis test of clinical endpoint will be performed at a significance level of 0.05 (2-sided) if the test of the surrogate endpoint is successful and 0.002 (2-sided) otherwise.
		
Part 2: Primary efficacy endpoint (sensitivity analyses 1)	The primary endpoint will be performed using the ITT and PP1 populations as sensitivity analyses.	Same as above	Same as above
Part 2: Primary efficacy endpoint (sensitivity analysis 2)	An assessment of primary endpoint will also be made using multiple imputation with informative censoring imputation model. Refer to Section 5.1.1.1.5.	Same as above	Multiple imputation with informative censoring imputation model

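### In the global analysis, the condition that releases full alpha to the Part 2 clinical endpoint is worded two ways, and the Part 2 threshold differs 25-fold between them if the primary succeeds and the key secondary fails

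*SAP*

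**What the plan says.** The plan works in two tiers. In the strong-evidence tier, 0.0012 goes to the surrogate side and 0.00005 to the clinical outcome endpoint, 0.00125 in total. In the study-success tier the split is 0.048 and 0.002, 0.05 in total. In both, success in Part 1 raises the clinical endpoint to the full level. The texts differ on what counts as success.

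- SAP 5.1.1.3.3 (multiple comparisons): the clinical endpoint "will be tested at the 0.00125 level if the tests of the surrogate endpoints (i.e., primary and key secondary) are successful". The same procedure applies in the 0.05 tier. SAP 5.1.1.1.7 says p-values "will be interpreted in accordance with the multiple comparisons procedure described in Section 5.1.1.3.3".
- SAP Table 5-14, in a row headed for both the global and the European analysis: the Part 2 test is "performed at a significance level of 0.00125 (2-sided) if the test of the surrogate endpoint is successful and 0.00005 (2-sided) otherwise". Protocol 12.3.2.2 uses the same words.
- Protocol synopsis: "the clinical outcome endpoint will be tested at 0.00125 level if the test of surrogate endpoint is successful".

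Usage elsewhere is mixed. Protocol 5.4 describes Part 1 as "Evaluate the surrogate endpoint of improvement in fibrosis of at least 1 stage", which is the primary endpoint only. SAP 5.1.1.3.1 sets out the global hierarchy (primary, then key secondary) and continues "These surrogate endpoints will be tested at the 0.0012 (2-sided) alpha level to manifest strong evidence from a single confirmatory study", which covers both. For Europe it states that "Part 1 testing is only for the region-specific primary endpoint, a binary endpoint"; SAP 4.2 lists no EU key secondary.

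**The concern.** The gate decides the significance level of the trial's clinical outcome test, so it should have one reading. If both Part 1 endpoints succeed, or the primary fails, the two wordings agree. If the primary succeeds and the key secondary fails, one wording gives Part 2 the full alpha and the other leaves it at the initial share, 25 times smaller in either tier.

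Part 1 will be unblinded and analysed long before Part 2 ends. Anyone choosing between the wordings at that point would already know whether the key secondary had failed.

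Error control is also at stake. Under a primary-only gate, the alpha freed by the primary is used twice: once for the key secondary at 0.0012 (0.048), and again to raise the clinical endpoint to 0.00125 (0.05). If both are confirmatory claims, strong familywise control is lost. The chain in SAP 5.1.1.3.3 uses it once.

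The change lists do not settle the matter. SAP 5.2.2 does not mention the gate. The SAP Section 8 entry for 5.1.1.3.3 says only that alpha control spans both parts.

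**Working it through.** **Inputs.** From SAP 5.1.2 and protocol 12.8: Part 1 with 800 CVC and 400 placebo; primary rates 25% and 15%; key secondary rates 8.6% and 2.2%; Part 2 with 367 events, hazard ratio 0.62 and 2:1 allocation. Alpha levels are from SAP 5.1.1.3.3.

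**The plan's own figures.**
- Alpha: 0.0012 + 0.00005 = 0.00125; 0.048 + 0.002 = 0.05.
- Part 1 power at two-sided 0.0012 (z = 3.239), unpooled variance. Primary: standard error √(0.15·0.85/400 + 0.25·0.75/800) = 0.0235, and Φ(0.10/0.0235 − 3.239) = 84.4% (stated 84%). Key secondary: standard error √(0.022·0.978/400 + 0.086·0.914/800) = 0.0123, power 97.4% (stated 97%). With pooled variance the two are 78.2% and 89.1%.
- Part 2 power: Φ(√(367·2/9)·|ln 0.62| − z) = Φ(9.031·0.478 − z) = Φ(4.317 − z). This gives 86.2% at 0.00125 (stated 85%) and 99.1% at 0.05 (stated 99%).

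The stated figures are reproduced. The problem is in the rule.

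**Part 2 power if the primary succeeds and the key secondary fails.**

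| Tier | Singular wording read as primary only | Gate in SAP 5.1.1.3.3 |
|---|---|---|
| Strong evidence | 0.00125: Φ(4.317 − 3.227) = 86.2% | 0.00005: Φ(4.317 − 4.056) = 60.3% |
| Study success | 0.05: Φ(4.317 − 1.960) = 99.1% | 0.002: Φ(4.317 − 3.090) = 89.0% |

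The alpha ratio is 0.00125/0.00005 = 0.05/0.002 = 25.

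**Familywise error with the key secondary in the family.** Worst case: the primary always rejects, the key secondary and clinical nulls are both true, and their statistics are independent.
- Primary-only gate: 1 − (1 − 0.0012)(1 − 0.00125) = 0.00245, and 1 − (1 − 0.048)(1 − 0.05) = 0.0956.
- Gate in 5.1.1.3.3: an error arises if the key secondary rejects, or if it does not and the clinical endpoint rejects at the low level. This gives 1 − (1 − 0.0012)(1 − 0.00005) = 0.00125, and 1 − (1 − 0.048)(1 − 0.002) = 0.0499.
- Primary-only gate with assumed correlation 0.5 between the two statistics: 0.0024 and 0.089. With 0.8: 0.0022 and 0.077.
- Primary-only gate, strict tier, primary rejecting with probability q rather than always: 0.00245q + 0.00005(1 − q), which is 0.0019 at q = 0.78 and 0.0021 at q = 0.84.

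**How often the readings part.** Simulation at the planning rates, key secondary responders nested within primary responders, unstratified two-sample z test. The table gives the chance that the key secondary fails given that the primary succeeds, as unpooled to pooled variance. SAP 5.2.1 reports 1293 randomized in Part 1; its table implies 1334 − 472 = 862 CVC and 666 − 235 = 431 placebo.

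| Part 1 size | At 0.0012 | At 0.048 |
|---|---|---|
| 1200 (800:400) | 2.1% to 5.9% | below 0.2% |
| 1293 (862:431) | 1.4% to 4.0% | below 0.1% |

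Unconditionally, the strict-tier figure at 1200 is 1.8% to 4.6%. These rest on the planned key secondary effect. If the CVC rate were 5.4% (my assumption: 2.2% plus half of the planned 6.4-point difference), the unconditional chance would be about 46% to 60% at 0.0012 and 17% to 22% at 0.048.

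**The case against.** A working rule already exists. SAP 5.1.1.3.3 names both endpoints, SAP 5.1.1.1.7 makes that section govern interpretation, and the gate it states controls error. The singular may be shorthand. Both documents label Part 1 as a whole by the surrogate endpoint in their design sections. Protocol 12.3.2.1 describes the two-test hierarchy and then uses the singular for the 0.0012 level, where SAP 5.1.1.3.1 has the plural. SAP 5.1.1.3.3 itself uses the singular for the initial allocation. The Table 5-14 row has to serve both the EU analysis, with one surrogate, and the global analysis, with two. The inflation figures need a primary-only gate, which no passage states outright. They also need the key secondary inside a family that the plan describes as lying between the surrogate and the clinical endpoint. At the planning rates, divergence is rare.

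Most of this stands, and it limits the point. The primary-only reading is an inference, the inflation is conditional on it, and 5.1.1.3.3 has the better claim to govern. The text of protocol 12.3.2.1 also breaks off in the copy reviewed, so its silence on the gate is not held against the plan. But no passage says that the singular means both endpoints, and protocol 5.4 uses it for the primary alone. Table 5-14 sits in the same SAP and gives its own rule for what happens otherwise, so the SAP's precedence over the protocol does not remove the conflict. Rarity depends on the key secondary effect being as large as planned.

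**Conclusion.** The concern holds for the global analysis. The rule that sets the Part 2 threshold has two readings, 25-fold apart when the primary succeeds and the key secondary fails. The cost in that case is 86% against 60% power in the strict tier and 99% against 89% in the study-success tier, assuming 367 events and a hazard ratio of 0.62.

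Loss of familywise control (up to 0.00245 and 0.096) follows only if the gate is read as primary-only and the key secondary is a confirmatory claim. There is no inflation under the global null, under the 5.1.1.3.3 gate, in the EU analysis, or if the family is only the primary and the clinical endpoint. The EU analysis has no conflict over its gate, although SAP 5.1.1.3.3 says it applies there too and its mention of a key secondary does not fit. The wording should be settled before Part 1 unblinding. Confidence in the wording conflict is high.

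**What to change.** Before Part 1 is unblinded, align the protocol synopsis, protocol 12.3.2.2 and SAP Table 5-14 with SAP 5.1.1.3.3. For the global analysis, state that Part 2 is tested at 0.00125 (0.05) only if both the primary and the key secondary are significant at 0.0012 (0.048), and otherwise at 0.00005 (0.002). Add one sentence to SAP 5.1.1.3.3 saying that the EU gate is its single surrogate endpoint.

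The cost is a few sentences in each document. The statistical price is that Part 2 keeps the smaller alpha if the key secondary fails. If the sponsor does not want that, a primary-only gate also keeps control, provided that no confirmatory claim is made for the key secondary and the plan says so.
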